5.5.2. Treatment Delay

For infusion-related reactions and immune-related AEs attributed to GS-1423, please follow Sections [5.5.3](#) and [5.5.4](#), respectively, for treatment delay guidance. For AEs attributed to mFOLFOX6, please follow [Appendix 6](#) for guidance.

Study treatment may also be delayed due to any AE, laboratory abnormality, or intercurrent illness which, in the judgment of the investigator, warrants a delay.

If an AE is attributed to only one study drug, it is at the Investigator's discretion to determine if the study drug(s) not attributed to the AE will be withheld based on the Investigator's assessment of risk-benefit of withholding one or more study drugs.

Subjects who have drug-related toxicities that meet the criteria for dose delay should have study drug treatment delayed until criteria to resume treatment are met. It is recommended to restart study drug treatment at the next scheduled administration.

Note: GS-1423 should be discontinued in subjects who experience any Grade ≥ 3 skin drug-related AE, suspected/confirmed Stevens-Johnson syndrome, or suspected/confirmed toxic epidermal necrolysis. See Section [5.5.6](#) for permanent treatment discontinuation criteria due to AEs.

5.5.3. Treatment of Infusion-Related Reactions

Acute infusion reactions (which can include, CRS, angioedema, or anaphylaxis) are different from allergic/hypersensitive reactions, although some of the manifestations are common to both AEs. Signs and symptoms usually develop during or shortly after drug infusion and generally resolve completely within 24 hours of completion of infusion. Signs/symptoms may include allergic reaction/hypersensitivity (including drug fever); arthralgia (joint pain); bronchospasm; cough; dizziness; dyspnea (shortness of breath); fatigue (asthenia, lethargy, malaise); headache; hypertension; hypotension; myalgia (muscle pain); nausea; pruritus/itching; rash/desquamation; rigors/chills; sweating (diaphoresis); tachycardia; tumor pain (onset or exacerbation of tumor pain due to treatment); urticaria (hives, welts, wheals); and vomiting.

For individual subjects, once the GS-1423 infusion rate has been decreased by 50% or interrupted due to an infusion-related reaction, it must remain decreased for all subsequent infusions for that subject. If the subject has a second infusion-related reaction that is Grade ≥ 2 at the slower infusion rate, infusion should be stopped, and the subject should discontinue treatment. If a subject experiences a Grade 3 or Grade 4 infusion-related reaction at any time, the subject must discontinue treatment ([Table 5-2](#)). If an infusion reaction occurs, all details about drug preparation and infusion must be recorded.

For the gastric cohort (Phase 1b Cohort 1), careful monitoring must be ensured for subjects with a history of allergic reactions to other platinum-based chemotherapy agents. In the event of anaphylactic shock symptoms, interrupt infusion immediately and initiate appropriate treatment. Resumption of oxaliplatin treatment following anaphylactic reaction is contraindicated.

Clinically significant, abnormal 12-lead safety electrocardiograms (ECGs) should be repeated. Subjects who have 2 consecutive ECGs showing a new absolute QTcF (Fridericia correction) duration > 500 ms, or a QTc > 60 ms over the corresponding baseline value must discontinue any medications that could prolong the QT interval (including oxaliplatin). Subject's concomitant medications should be reviewed to determine a potential etiology for the ECG changes. Appropriate intervention (ie, cardiology evaluation, telemetry monitoring, management of electrolyte abnormalities) in response to treatment-emergent QT interval prolongation should be initiated.

Should infusion reaction be considered a significant safety issue by the SRT, the SRT might decide to recommend premedication with an antihistamine and acetaminophen approximately 30 to 60 minutes before each dose of GS-1423 (eg, 25-50 mg diphenhydramine, 500-1000 mg acetaminophen or equivalent dose of antipyretic).). This regimen may be modified based on local treatment standards and guidelines, as appropriate.

Table 5-2 shows treatment guidelines for subjects who experience an infusion reaction associated with administration of GS-1423.

Subjects receiving GS-1423 should be monitored for infusion reactions. This includes the measurement of vital signs prior to each infusion commencing, at the end of each infusion, and for the first 2 cycles, 1 hour (\pm 15 minutes) after the end of the GS-1423 infusion. Thereafter, the final vital signs can be taken 30 minutes (-10/+20 minutes) after the end of the GS-1423 infusion. Subjects will remain in the clinic under close supervision for the duration of this monitoring period. Subjects with mild or moderate infusion reactions may receive GS-1423 with close monitoring. Premedication with an antipyretic or antihistamine for subsequent treatment administration may be considered. For severe infusion reactions, GS-1423 infusion must be discontinued, and appropriate medical therapy should be administered.

Subjects who do not experience any infusion-related toxicity Grade 1 or higher during or after the infusion may be released from monitoring after 1 hour if they are otherwise stable. Subjects with any infusion-related toxicity must be managed as per the guidelines in **Table 5-2**, and monitoring will continue until any infusion-related toxicity has abated to less than Grade 1 and at least 1 hour has passed from the completion of the entire infusion and flushing the line. All subjects will be given information on and instructions regarding both infusion-related toxicity, which is expected to be most likely in the hour after completion of the infusion, and immune-related AEs (irAEs) before leaving the study site.

Table 5-2. GS-1423 Infusion-Related Reactions Management Guidelines

| CTCAE Grade | Treatment | Premedication at Subsequent Dose Administration |
|--|---|--|
| Grade 1 Mild transient reaction; infusion interruption not indicated; intervention not indicated. | Increase monitoring of vital signs as medically indicated until the subject is deemed medically stable in the opinion of the investigator. | None. |
| Grade 2 Requires infusion interruption but responds promptly to symptomatic treatment (eg, antihistamines, nonsteroidal anti inflammatory drugs [NSAIDs], narcotics, IV fluids); prophylactic medications indicated for \leq 24 hours. | 
Stop infusion and monitor symptoms. Additional appropriate medical therapy may include but is not limited to the following:
 
 IV fluids Antihistamines NSAIDs Acetaminophen Narcotics 
Increase monitoring of vital signs as medically indicated until the subject is deemed medically stable in the opinion of the investigator. If symptoms resolve within 1 hour of stopping drug infusion, the infusion may be restarted at 50% of the original infusion rate. Otherwise, dose administration will be held until symptoms resolve, and the subject should be premedicated for the next scheduled dose. Subjects who develop Grade 2 toxicity despite adequate premedication should be permanently discontinued from further study drug administration.
 | 
Subject may be premedicated prior to infusion with the following:
 
 Diphenhydramine 25-50 mg PO (or equivalent dose of antihistamine). Acetaminophen 500-1000 mg PO (or equivalent dose of antipyretic). |
| Grade 3 or 4 Grade 3 Prolonged (ie, not rapidly responsive to symptomatic medication and/or brief interruption of infusion); recurrence of symptoms following initial improvement; hospitalization indicated for other clinical sequelae (eg, renal impairment, pulmonary infiltrates). Grade 4 Life threatening; pressor or ventilatory support indicated. | 
Stop infusion. Additional appropriate medical therapy may include but is not limited to:
 
 IV fluids Antihistamines NSAIDs Acetaminophen Narcotics Oxygen Pressor Corticosteroids Epinephrine 
Increase monitoring of vital signs as medically indicated until the subject is deemed medically stable in the opinion of the investigator. Hospitalization may be indicated. Subject is permanently discontinued from further study drug administration.
 | No subsequent dosing. |

CTCAE Common Terminology Criteria for Adverse Events; IV intravenous; NSAID nonsteroidal anti inflammatory drug; PO orally

5.5.4. Management of Potential Immune-Related Adverse Events

Immune-related AEs may be associated with immuno-oncology agents such as GS-1423 and will be categorized as AEs of interest in this study. An irAE is defined as an AE of unknown etiology, that is potentially associated with study drug exposure and is consistent with an immune-mediated phenomenon. Efforts should be made to rule out other etiologies prior to labeling an AE of clinical interest. Early recognition and management of irAEs may mitigate

severe toxicity. Investigators should also monitor subjects closely for potential irAEs, which may manifest after weeks of treatment, at the earliest. Such events may consist of persistent rash, diarrhea, colitis, autoimmune hepatitis, pneumonitis, encephalitis, arthritis, glomerulonephritis, cardiomyopathy, or uveitis and other inflammatory eye conditions.

Management algorithms have been developed to assist investigators in assessing and managing the following groups of irAEs: dermatological, gastrointestinal, pulmonary, hepatic, endocrine renal, and neurological, among others.

Adverse events (both non-serious and serious) associated with drug exposure and consistent with an immune phenomenon may represent an immunologic etiology. These irAEs may be predicted based on the nature of the study drugs, their mechanism of action, and reported experience with immunotherapies that have a similar mechanism of action. An irAE can occur any time from shortly after the first dose to several months after the last dose of treatment. Particular attention should be paid to AEs that may be suggestive of potential irAEs, as outlined below.

5.5.4.1. Dermatological irAEs

Rule out non-inflammatory causes. If a non-inflammatory cause is identified, treat accordingly and continue therapy per protocol.

Table 5-3. Dermatological irAE Management Algorithm

| Dermatological irAEs | | |
|---|---|---|
| CTCAE Grade of Rash | Management | Follow-up |
| Grade 1-2 Covering \leq 30% body surface area | Symptomatic therapy (eg, antihistamines, topical corticosteroids). Continue GS-1423 therapy per protocol. | If persists > 1 to 2 weeks or recurs: Consider skin biopsy. Delay GS-1423 therapy. Consider 0.5-1 mg/kg/day methylprednisolone IV or oral equivalent. Once improving, taper corticosteroids over ≥ 1 month; consider prophylactic antibiotics for opportunistic infections; and resume GS-1423 therapy per protocol. If worsens: Treat as Grade 3-4. |
| Grade 3-4 Covering $>$ 30% body surface area; life-threatening consequences | Delay or discontinue GS-1423 therapy per protocol. Consider skin biopsy. Dermatology consult 1-2 mg/kg/day methylprednisolone IV or IV equivalent. | If improves to Grade 1: Taper corticosteroids over ≥ 1 month; add prophylactic antibiotics for opportunistic infections. Resume GS-1423 therapy per protocol. |

CTCAE Common Terminology Criteria for Adverse Events; irAE immune related adverse event; IV intravenous.

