5.5.6. Permanent Treatment Discontinuation

Study drug treatment must be discontinued for drug-related AEs described in [Table 5-10](#). Non-AE reasons for study treatment discontinuation can be found in Section [6.10.1](#).

Table 5-10. Drug-Related Adverse Events Requiring Discontinuation of GS-1423

| Toxicity Category* | Qualifying Severity/Duration |
|--------------------|--|
| Ophthalmic | 
• Grade 2 uveitis, blurred vision, eye pain, and/or reduction of visual acuity that does not respond to topical therapy and does not improve to Grade 1 severity within 2 weeks OR requires systemic treatment• Grade 3 or higher uveitis |
| Gastrointestinal | 
• Grade 3 or higher diarrhea, colitis |
| Neurologic | 
• Grade 3 or higher neurologic toxicities |
| Dermatologic | 
• Grade 3 or higher skin AE, suspected Stevens-Johnson syndrome, or toxic epidermal necrolysis |
| Pulmonary | 
• Grade 2 pneumonitis or interstitial lung disease that does not improve after 2 weeks or worsening despite dose delay and systemic corticosteroids (see Table 5-5)• Grade 3 or higher pneumonitis |
| Endocrinopathies | 
• Grade 3 endocrinopathies not adequately controlled with physiologic hormone replacement• Grade 4 or higher endocrinopathies |
| Hypersensitivity | 
• Grade 3 or higher bronchospasm, hypersensitivity reaction, or infusion-related reaction |

| Toxicity Category* | Qualifying Severity/Duration |
|--------------------|--|

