| Laboratory | 
Thrombocytopenia
 
• Grade 3 thrombocytopenia lasting > 7 days or associated with clinically significant bleeding (i.e. requires hospitalization, transfusion of blood products, or other urgent medical intervention)• Grade 4 thrombocytopenia 
Neutropenia
 
• Grade 4 neutropenia lasting > 7 days 
Electrolyte Abnormalities
 
• Grade 4 electrolyte abnormalities with clinical sequelae• Grade 4 electrolyte abnormalities unable to be corrected with supplementation/appropriate management within 72 hours of onset 
Liver Function Abnormalities (see Table 5-6)
 
• AST or ALT > 5 × ULN• Total bilirubin > 3 × ULN• Concurrent AST or ALT > 3 × ULN AND total bilirubin > 2 × ULN lasting > 7 days |
| Other | 
• Grade 2 or 3 adverse event (laboratory or non-laboratory) that does not resolve in ≤ 12 weeks• Recurrence of Grade 3 or higher adverse event (laboratory or non-laboratory)• Grade 4 non-hematologic adverse event |

* AE must be study drug related for discontinuation reasons to apply

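### Table 5-3 allows GS-1423 to be resumed after a drug-related Grade 3-4 immune-related rash improves to Grade 1, while Sections 5.5.2, 5.5.6 and 6.10.1 end treatment for the same event

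*Protocol*

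**What the plan says.** Protocol Section 5.5.4.1, Table 5-3, has one row for Grade 3-4 rash, covering more than 30% of body surface or life-threatening consequences. Its management cell begins "Delay or discontinue GS-1423 therapy per protocol". Its follow-up cell, for a rash that improves to Grade 1, calls for a steroid taper and then says "add prophylactic antibiotics for opportunistic infections. Resume GS-1423 therapy per protocol".

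Section 5.5.5 lets dosing restart once a drug-related event is back to Grade 1 or baseline. It then lists exceptions, none of which concerns skin.

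Other sections point the other way:

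- The note in Section 5.5.2 says "GS-1423 should be discontinued in subjects who experience any Grade ≥ 3 skin drug-related AE".
- Section 5.5.6 opens with "Study drug treatment must be discontinued for drug-related AEs described in" Table 5-10. The dermatologic entry in that table is "Grade 3 or higher skin AE, suspected Stevens-Johnson syndrome, or toxic epidermal necrolysis", with no condition on duration or improvement. A footnote limits the table's scope: "AE must be study drug related for discontinuation reasons to apply".
- Section 6.10.1 repeats that the events in Section 5.5.6 must end study drug.

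**The concern.** A site faced with a severe immune-related rash would naturally open Table 5-3, because Section 5.5.2 refers immune-related events to Section 5.5.4 for guidance on delay. That page shows a route back to dosing. Sections 5.5.6 and 6.10.1 show none.

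Two things are at stake. The first is consistency of re-exposure after a severe drug-related skin reaction in a first-in-human study. The second is consistency of reporting. SAP Section 7.1.6.1 summarises treatment-emergent events leading to premature discontinuation separately from those leading to temporary interruption, and SAP Section 4.3 summarises important protocol deviations. Which of these a given rash falls into could depend on which protocol page the site followed.

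**Working it through.** No arithmetic applies. The check is to set the passages side by side and follow one event through them.

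| Place in protocol | Event covered | Instruction | Route back to dosing |
|---|---|---|---|
| Table 5-3, Grade 3-4 row | Immune-related rash, Grade 3-4 | Hold or stop | Yes, on improvement to Grade 1 |
| Section 5.5.5 | Drug-related events in general | Restart permitted at Grade 1 or baseline | Yes; no skin exception listed |
| Section 5.5.2, note | Drug-related skin event, Grade 3 or higher | Should stop | None |
| Section 5.5.6, Table 5-10, dermatologic row | Drug-related skin event, Grade 3 or higher | Must stop | None |
| Table 5-10, 'Other' row | Drug-related non-hematologic event, Grade 4 | Must stop | None |
| Section 6.10.1 | Events in Section 5.5.6 | Must stop | None |

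1. **Do the rows cover the same event?** Largely. Section 5.5.4 defines an immune-related event as one "that is potentially associated with study drug exposure and is consistent with an immune-mediated phenomenon". Section 7.2.1 counts an event as related when there is a reasonable chance that the drug caused it. Section 5.5.4.1 takes non-inflammatory causes out of the algorithm. The overlap is large but not complete, since an event handled under Table 5-3 may still be judged unrelated.

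2. **Does 'per protocol' settle it?** No. Followed to Table 5-10, the words mean stop. Followed to Section 5.5.5, the section on resuming treatment, they support a restart at Grade 1. Section 5.5.5 does refer to the discontinuation criteria of Section 5.5.6 for combined liver abnormalities, but makes no such reference for skin.

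3. **How do the other algorithms read?** The gastrointestinal, pulmonary, hepatic and neurological tables say to discontinue at Grade 3-4 and give no resume step, in line with Table 5-10. The renal table allows delay and resumption at Grade 2-3, but Table 5-10 has no renal row. The endocrine table uses the same delay-or-discontinue phrase for suspected adrenal crisis, in an ungraded row without a resume step. For Grade 3 endocrinopathy, Table 5-10 requires discontinuation only if hormone replacement does not control it adequately.

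4. **Trace one subject.** A drug-related Grade 3 immune-related rash improves to Grade 1. Under Table 5-3 and Section 5.5.5 the subject may resume. Under Section 5.5.2 the subject should have stopped, and under Sections 5.5.6 and 6.10.1 must have stopped. For a Grade 4 rash, two entries of Table 5-10 apply.

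**The case against.** The best defence is that the documents signal which text binds. Section 5.5.4 presents the algorithms as help for investigators. Section 5.5.2, having sent the reader there, adds a note singling out Grade 3 or higher drug-related skin events and pointing to Section 5.5.6. Sections 5.5.6 and 6.10.1 are mandatory in tone, and both cells of the Table 5-3 row defer to the protocol. A careful site would probably find the stricter text. This lowers the chance of divergent handling. It does not remove the conflict, because Section 5.5.5 is also protocol text and supports resumption.

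A reader might infer that, if Table 5-10 governs, the delay and resume wording could never apply to a drug-related rash. The documents do not support that. The Grade 1-2 row of Table 5-3 sends a worsening rash to the Grade 3-4 row, so a rash that worsens only from Grade 1 to Grade 2 can be managed there without meeting Table 5-10. The row can also serve events judged unrelated. These readings give the row some legitimate use, but they do not reconcile it with Table 5-10 for a rash that is both drug-related and Grade 3-4.

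Nor is the dermatological table alone in allowing delay for a severe event: the renal and endocrine tables do so too. What sets the Grade 3-4 rash row apart is an explicit resume step set against a Table 5-10 entry that carries no condition.

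**Conclusion.** The contradiction is real and lies in current text. It is confined to subjects whose rash is drug-related, reaches Grade 3-4 and then improves to Grade 1; only they reach the resume instruction. It would be too strong to say that every subject with a drug-related Grade 3-4 rash is affected by the resume step.

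In practice the relevant population is Part A monotherapy, planned for up to 53 subjects, because SAP Section 1 states that the study ended at completion of Part A and that Part B and Phase 1b will not be initiated. A reader might cite protocol Section 1.6 as showing that rash is an expected toxicity of the chemotherapy combination. That section only raises rash as a possibility, and the combination cohort was not opened.

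The documents report no rash counts, so the number of affected subjects is unknown and no numerical effect is claimed. The affected SAP outputs are descriptive. Dose-limiting toxicity has its own definition in Section 3.2.3.3, which does not refer to Table 5-3, and no effect on that endpoint is claimed. The mandatory force of the stop rule rests on Sections 5.5.6 and 6.10.1; Section 5.5.2 says only that treatment should stop.

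**What to change.** Reconcile the Grade 3-4 row of Table 5-3 and Section 5.5.5 with Section 5.5.2, Section 5.5.6 with Table 5-10, and Section 6.10.1, so that all give the same instruction for a drug-related Grade 3-4 rash. State in the row whether it also covers rashes that worsen only to Grade 2 and events judged unrelated. Which clinical rule to adopt is for the sponsor.

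The cost is protocol wording only. If the protocol is not amended now that Part A is complete, the sponsor should document which instruction governed. Any affected cases should then be classified consistently as interruption, discontinuation or deviation before the data are finalised.

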5.5.4.2. Gastrointestinal irAEs

Rule out non-inflammatory causes. If a non-inflammatory cause is identified, treat accordingly and continue therapy. Opiates/narcotics may mask symptoms of perforation. Infliximab should not be used in cases of perforation or sepsis.

Table 5-4. Gastrointestinal irAE Management Algorithm

| Gastrointestinal irAEs | | |
|--|--|---|
| CTCAE Grade of Diarrhea / Colitis | Management | Follow-up |
| Grade 1 Diarrhea: < 4 stools/day over baseline. Colitis: asymptomatic. | Continue GS-1423 therapy per protocol. Symptomatic treatment. | Close monitoring for worsening symptoms. Educate subject to report worsening immediately. Consider symptomatic treatment including hydration, electrolyte replacement, dietary changes (eg, American Dietetic Association colitis diet), and loperamide. If worsens: Treat as Grade 2 or 3-4. |
| Grade 2 Diarrhea: 4-6 stools per day over baseline; IV fluids indicated < 24 h; not interfering with activities of daily living (ADL). Colitis: abdominal pain; blood in stool. | Delay GS-1423 therapy per protocol. Symptomatic treatment. | If improves to Grade 1: Resume GS-1423 therapy per protocol. If persists > 5 to 7 days or recurs: 0.5-1 mg/kg/day methylprednisolone or equivalent. When symptoms improve to Grade 1, taper corticosteroids over \geq 1 month; consider prophylactic antibiotics for opportunistic infections; resume GS-1423 therapy per protocol. If worsens or persists > 3 to 5 days with oral corticosteroids: Treat as Grade 3-4. |
| Grade 3-4 Diarrhea (Grade 3): \geq 7 stools per day over baseline; incontinence; IV fluids \geq 24 h; interfering with ADL. Colitis (Grade 3): severe abdominal pain, medical intervention indicated, peritoneal signs. Grade 4: life-threatening, perforation | Discontinue GS-1423 therapy per protocol. 1-2 mg/kg/day methylprednisolone IV or equivalent. Add prophylactic antibiotics for opportunistic infections. Consider lower endoscopy. | If improves: Continue corticosteroids until Grade 1, then taper over \geq 1 month. If persists > 3 to 5 days or recurs after improvement: Add infliximab 5 mg/kg (if no contraindication). Note: Infliximab should not be used in cases of perforation or sepsis. |

ADL activities of daily living; CTCAE Common Terminology Criteria for Adverse Events; irAE immune related adverse event; IV intravenous.

